## 5.3 DATA FROM PARENT STUDIES

Data referring to the disease history, as well as the height, were not collected in the study EDC but remained in the databases of the parent studies where the patients are coming from.

In addition, the data from the end of the treatment (or last visit) in the parent studies, will be extracted by the parent studies databases and transferred by the sponsor to the CRO. The date of the EOT visit from the parent study will be matched with the date of the baseline (W1D1) to guarantee the proper correspondence. The cases with a discrepancy exceeding one week between the two dates will be evaluated case by case.

For disease history they are the following ones:

- Time (months) to first study osilodrostat dose since diagnosis
- Classification at time of diagnosis
- Cushing's Disease Status
- Any previous surgery
- Any previous, non-LCI, treatments for Cushing's disease
- Any previous pituitary irradiation
- Baseline mean UFC.

---

Study Code: CLCI699C2X01B

---

For W1D1 visit the data to be transferred will regard the following topics:

- Vital signs (domain VS)
- ECG (domain EG)
- MRI (domains PR, FA)
- Laboratory (domain LB)

The data will be extracted as SAS datasets as close as possible to the domain structures reported in attachment 8.2.

## 6 ANALYSIS POPULATIONS

### 6.1 RELEVANT PROTOCOL DEVIATIONS

Protocol deviations will be categorized and tabulated overall and by indication and formulation into the following categories per ICH guidelines for CSR-reportable protocol deviations:

- Patient developed study/treatment withdrawal criteria during the study, but was not withdrawn
- Patient received the wrong treatment or incorrect dose
- Patient took an excluded concomitant medication
- Patient did not satisfy the entry criteria

Other important deviations may also be identified and summarized, as necessary, which may impact the scientific value of the trial.

All protocol deviations will be specified in the Study Specification Document (SSD).

All protocol deviations will be listed overall and by indication and formulation using Safety Set.

### 6.2 DEFINITION OF POPULATIONS FOR ANALYSIS

#### 6.2.1 Full Analysis Set

6.2.2 For this study, the definition of FAS is the same as the Safety Set and in the tables the Safety Set will be indicated. Safety Set

The Safety Set includes all patients who received at least one dose of study medication (Osilodrostat) after enrolling into the roll-over protocol.

#### 6.2.3 Subgroup of interest

Not Applicable

## 7 PLANNED ANALYSES

### 7.1 ANALYSIS OF THE PRIMARY OBJECTIVE

The primary objective is to evaluate long term safety as assessed by the occurrence of AEs / SAEs.

---

Study Code: CLCI699C2X01B

### 7.1.1 Primary endpoint

The assessment of safety will be based mainly on the frequency and severity of AEs, AESI and SAEs. See also Section 7.5.

### 7.1.2 Statistical hypothesis, model, and method of analysis

The primary endpoint will be summarized descriptively, overall no formal analysis will be performed. No hypothesis will be tested.

## 7.2 ANALYSIS OF SECONDARY EFFICACY OBJECTIVE(S)

The secondary objective of the study is to evaluate clinical benefit as assessed by the investigator.

### 7.2.1 Secondary endpoints

Proportion of patients with clinical benefit as assessed by the investigator will be summarized at scheduled visits. Clinical benefit will be summarized overall using the Safety Set.

## 7.3 EXTENT OF EXPOSURE

Definitions of duration of exposure, cumulative dose, average daily dose, as well as intermediate calculations, include:

Osilodrostat:

- Duration of exposure (weeks): (min (last date of rollover study drug, date of death, date of data cut-off) – first date of rollover study drug + 1)/7
- Cumulative dose (µg): total dose of study drug taken by a patient in the rollover study
- Number of dosing days (days): duration of exposure \*7 – number of zero dose days
- Average daily dose (µg/day): cumulative dose (µg) / number of dosing days (days)

## 7.4 SAFETY ANALYSIS

Safety analyses will be performed on the Safety Set. The assessment of safety will be based mainly on the frequency of AEs, AESI and SAEs.

### 7.4.1 Adverse events (AEs)

Treatment emergent AEs are defined as those that started on or after the study medication, or those that started before study medication but worsened afterwards. AEs starting after 30 days after last dose of Osilodrostat treatment are not considered treatment emergent AEs.

Summary tables for adverse events (AEs) have to include only AEs that started or worsened during the on-treatment period, the treatment-emergent AEs. However, all safety data (including those from the post-treatment periods) will be listed and those collected during the post-treatment period are to be flagged.

The incidence of treatment-emergent adverse events (new or worsening from baseline) will be summarized by system organ class and/or preferred term, severity based on CTCAE grades (version 4.03 or higher), type of adverse event, relation to study treatment. The summary will include AEs regardless of study-drug relationship. The same analysis will be repeated for SAEs.

All treatment emergent AEs and SAEs will be listed. In this listing, the information on the relationship to study treatment will be included.

---

Study Code: CLCI699C2X01B

Adverse events will be coded using the Medical dictionary for regulatory activities (MedDRA) terminology using the latest available MedDRA version at the time of the analyses and the information of MedDRA version will be specified in the footnote of relevant outputs.

The following selection of AEs will be listed and summarized separately using Safety Set. AEs will be summarized for all grades and for grade 3 or 4 side-by-side.

- AEs
- SAEs
- AEs leading to study drug discontinuation
- AEs requiring dose adjustment or interruption
- AEs requiring additional therapy
- Adverse events of special interest (AESI)

For the legal requirements of ClinicalTrials.gov and EudraCT, two required tables on treatment-emergent adverse events which are not serious adverse events with an incidence greater than 2% and on treatment-emergent serious adverse events and SAE suspected to be related to study treatment will be provided by system organ class and preferred term on the Safety Set population.

If for a same patient, several consecutive AEs (irrespective of study treatment causality, seriousness and severity) occurred with the same SOC and PT:

- A single occurrence will be counted if there is  $\leq 1$  day gap between the end date of the preceding AE and the start date of the consecutive AE
- More than one occurrence will be counted if there is  $> 1$  day gap between the end date of the preceding AE and the start date of the consecutive AE

For occurrence, the presence of at least one SAE / SAE suspected to be related to study treatment / non SAE has to be checked in a block e.g., among AE's in a  $\leq 1$  day gap block, if at least one SAE is occurring, then one occurrence is calculated for that SAE.

The number of deaths resulting from SAEs suspected to be related to study treatment and SAEs irrespective of study treatment relationship will be provided by SOC and PT.

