6.1.5 Treatment duration

The study is expected to remain open for approximately 5 years (or until 31-December-2023 in the UK) from FPFV. Subjects will continue to be treated in the roll-over study until they are no longer benefiting from their osilodrostat treatment as judged by the Investigator or until osilodrostat is commercially available or until one of other discontinuation criteria is met (please refer to [Section 9.1.1](#)). At every quarterly visit (every 12 weeks \pm 2 weeks), the Investigator is required to confirm that the subject continues to have clinical benefit and can continue receiving study treatment. A subject will reach the end of the roll-over study when osilodrostat treatment is permanently discontinued.

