9.1 Discontinuation

9.1.1 Discontinuation of study treatment

Discontinuation of study treatment for a subject occurs when study treatment is stopped earlier than the protocol planned duration, and can be initiated by either the subject or the investigator.

The investigator must discontinue study treatment for a given subject if, he/she believes that continuation would negatively impact the subject's well-being. Study treatment must be discontinued under the following circumstances:

- Emergence of the following adverse events:
 - Hypertension defined as office mean sitting systolic BP > 180 mmHg or mean sitting diastolic BP > 110 mmHg (confirmed and persistent, persistent is defined as unresolved with osilodrostat dose and/or other concomitant medication changes)
 - Any of the following laboratory abnormalities (confirmed):
 - Hyperkalemia (serum potassium > 6.0 mmol/L).
 - Hypokalemia (serum potassium < 2.8 mmol/L).
 - Any of the following laboratory abnormalities (confirmed and persistent):
 - Hyperkalemia (serum potassium > 5.5 mmol/L).
 - Hypokalemia (serum potassium < 3.0 mmol/L).
 - Hyponatremia (serum potassium < 130 mmol/L).
 - AST or ALT > 3.0 x ULN combined with total bilirubin > 2.0 1 ULN without evidence of cholestasis.
 - QTcF > 500 msec, if confirmed by a cardiologist (see [Section 6.5.1.2](#)),
 - QTcF > 480 msec or QTcF increase is > 60 msec compared to baseline if the investigator determines it is no longer safe for the patient to continue in the study, based on ECGs, cardiac examination, and recommendation from a cardiologist.
 - Pituitary tumor growth, if the tumor is < 2mm from the optic chiasm, or symptoms of actual compression of the optic chiasm emerge (visual field loss, cranial nerve palsies, diplopia) confirmed by MRI of the pituitary.
 - Protocol deviations
 - Lost to follow-up
 - Study terminated by the sponsor
 - Administrative problems
 - Physician decision
 - Subject/guardian withdraw consent
 - Subject has completed treatment based on study duration

When current treatment becomes commercially available in the applicable country, the patient will be withdrawn from the study.

- Pregnancy
- Use of prohibited treatment as per recommendations in the prohibited treatment section
- Any situation in which study participation might result in a safety risk to the subject

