12.5.1.2 Adverse events (AEs)

Summary tables for adverse events (AEs) will include only AEs that started or worsened during the on-treatment period, the ***treatment-emergent*** AEs.

The incidence of treatment-emergent adverse events (new or worsening from baseline) will be summarized by system organ class and or preferred term, severity (based on CTCAE grades), type of adverse event, relation to study treatment.

Serious adverse events, non-serious adverse events during the on-treatment period will be tabulated.

All deaths (on-treatment and post-treatment) will be summarized.

All AEs, deaths and serious adverse events (including those from post-treatment periods) will be listed and those collected during post-treatment period will be flagged.

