#### Tables

- Patient disposition (FAS)
- Demographics and baseline characteristics (FAS)
- Disease history (FAS)
- Duration of exposure to study drug during the overall study period excluding the parent study (Safety Set)
- Dose summary during the overall study period excluding the parent study (Safety Set)

---

Study Code: CLCI699C2X01B

- Dose summary during the overall study period including the parent study (Safety Set) \*
- Overview of adverse events (Safety Set)
- Adverse events, regardless of study drug relationship, by system organ class (Safety Set)
- Adverse events, regardless of study drug relationship, in at least 10% patients (All Patients all grades) by preferred term (Safety Set)
- Adverse events, suspected to be study drug related, in at least 5% patients (All Patients all grades) by preferred term (Safety Set)
- Serious adverse events, regardless of study drug relationship, by preferred term (Safety Set)
- Serious adverse events, suspected to be study drug related, by preferred term (Safety Set)
- Adverse events of special interest, regardless of study drug relationship - Adrenal hormone precursor accumulation-related AEs (Safety Set)
- Adverse events of special interest, regardless of study drug relationship - Hypocortisolism-related AEs (Safety Set)
- Adverse events of special interest, regardless of study drug relationship - Arrhythmogenic potential AEs (Safety Set)
- Adverse events of special interest, regardless of study drug relationship - Pituitary tumour enlargement-related AEs (Safety Set)
- Adverse events of special interest, regardless of study drug relationship - QT prolongation AEs (Safety Set)

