### 2.3.1 Timing of interim analyses and design adaptations

Interim analyses have been performed by the CRO at the following time points:

- Q3 2021
- Q1 2022
- Q1 2023

Further time points might be added until the end of the study as needed.

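### AE frequency, the primary endpoint, is planned without a person-time denominator, although the design makes follow-up unequal

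*SAP*

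**What the plan says.** The primary endpoint is the frequency and severity of AEs and SAEs (protocol Table 2-1, SAP Table 5-1). SAP 7.1.1 adds AESIs: "The assessment of safety will be based mainly on the frequency and severity of AEs, AESI and SAEs".

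The summary measure is incidence. SAP 7.4.1: "The incidence of treatment-emergent adverse events (new or worsening from baseline) will be summarized by system organ class and/or preferred term". Protocol 12.5.1.2: "The incidence of treatment-emergent adverse events (new or worsening from baseline) will be summarized by system organ class and or preferred term". SAP 4.1 presents categorical data as counts with percentages, and the interim AE tables in SAP 2.3 select terms by percentage of patients (10%, or 5% for related events). SAP 7.4.1 also has a rule for counting repeat occurrences, within its registry tables, and SAP 7.4.6 summarises deaths.

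Exposure is defined in SAP 7.3 as running from the first roll-over dose to the minimum of "last date of rollover study drug, date of death, date of data cut-off". It is tabulated in its own right (SAP 2.3, protocol 12.3) and used for dosing days and average dose. It is not a denominator for any AE count. Protocol 12.4.3 marks the handling of censoring and discontinuation for the primary endpoint as not applicable.

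On follow-up, protocol 6.1.5 states: "The study is expected to remain open for approximately 5 years (or until 31-December-2023 in the UK) from FPFV". Patients leave earlier on loss of benefit (protocol 3.1) and under protocol 9.1.1: "When current treatment becomes commercially available in the applicable country, the patient will be withdrawn from the study". The amendment rationales record 23 patients enrolled by 29 January 2019 and 100 by 8 April 2020.

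**The concern.** The percentage of patients with at least one event depends on two things: how often events occur and how long patients are watched. Here the second varies between patients by design, and no planned table separates the two. The same 20% could mean a high rate over a short time or a low rate over a long one.

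This matters for the study's stated purpose, long-term safety, and for the use made of the results. The interim analyses feed PSURs at a regulator's request (SAP 2.3). Three have been done (Q3 2021, Q1 2022, Q1 2023), and SAP 2.3.1 says: "Further time points might be added until the end of the study as needed". Once enrolment has stopped, the cumulative percentage with an event can only rise or stay level from one cut to the next. A reader of successive reports could not tell growing risk from growing exposure. For a rare AESI with no events, the crude table would not show how much observation stands behind the zero.

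**Working it through.** The documents give no AE rate, no sample size calculation and no distribution of time on study, so there is no planned figure to reproduce. What can be checked is how far a crude percentage moves with follow-up at a fixed event rate.

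**Dates (from the documents)**
- 29 January 2019: 23 enrolled (Amendment 01 rationale).
- 8 April 2020: 100 enrolled (Amendment 02 rationale). At least 77 of these 100 entered after the first date (100 − 23).
- 9 January 2020: European approval (protocol 1.2.1.2).
- 31 December 2023: UK end date (protocol 6.1.5).

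**Assumptions**
- A constant first-event rate r, at 5, 20 or 40 per 100 patient-years.
- 31 December 2023 as a common end.
- No market-access exit before the first approval.
- The 30-day tail after last dose is ignored.

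**Follow-up times (days / 365.25)**
- 29 Jan 2019 to 9 Jan 2020: 345 / 365.25 = 0.94 years.
- 8 Apr 2020 to 31 Dec 2023: 1362 / 365.25 = 3.73 years.
- 29 Jan 2019 to 31 Dec 2023: 1797 / 365.25 = 4.92 years.

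**Crude percentage = 1 − exp(−r × t)**

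| Rate per 100 patient-years | 0.94 y | 3.73 y | 4.92 y | Half at 0.94 y, half at 4.92 y |
|---|---|---|---|---|
| 5 | 4.6% | 17.0% | 21.8% | 13.2% |
| 20 | 17.2% | 52.6% | 62.6% | 39.9% |
| 40 | 31.5% | 77.5% | 86.0% | 58.7% |

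The two right-hand follow-up times (3.73 and 4.92 years) differ by entry date alone. The 0.94-year column is the extreme: exit on the day of approval.

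**The same percentage read backwards.** With 20 of 100 patients having an event, the rate is 20.0 per 100 patient-years (exact Poisson 95% CI 12.2 to 30.9) over 100 patient-years at risk, and 5.0 (3.1 to 7.7) over 400.

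**A rare AESI: 0 events in 100 patients.** The exact upper 95% limit for the percentage is 1 − 0.025^(1/100) = 3.6%, whatever the follow-up. The exact Poisson upper limit is 3.689 events. At a mean of 0.94 years that is 3.689 / 94.5 = 3.9 per 100 patient-years; at 4.92 years it is 3.689 / 492.0 = 0.75.

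**Why an overall rate is not enough.** If the rate is 20 in year 1 and 10 afterwards, the overall first-event rate over 4 years is 13.0. If it is 10 and then 20, the overall rate is 16.8. Neither shows the change, hence a split by year.

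**Why any AE needs a different measure.** In the earlier Cushing's disease study, all 12 Part I patients and all but one of 19 in Part II had an AE (protocol 1.2.1.2.2). At an assumed 200 first events per 100 patient-years, exp(−2) = 13.5% are event-free at 1 year and exp(−4) = 1.8% at 2 years. A yearly first-event rate for any AE would soon have almost nobody at risk, so total events are needed.

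**The case against.** The study is single-arm and descriptive, with no hypothesis, so no comparison between groups is distorted. Exposure is tabulated, SAP 2.3 allows further interim outputs, and the stored dates would let anyone add rates later. All of this stands, and it limits the weight of the point. It does not remove it. Summary exposure does not give time to first event. SAP 7.3 exposure also stops at last dose, while the treatment-emergent window runs 30 days longer, so dividing one table by the other gives the wrong denominator.

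Four stronger readings are tempting and not supported:

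- That AEs are reported only as crude incidence. The SAP also counts repeat occurrences and deaths; what is missing is a time denominator.
- That follow-up is known to differ widely, or that 17.2% v 62.6% is the expected distortion. Unequal follow-up follows from the entry dates and exit rules, but its spread is not given. Approval is not commercial availability, and no launch dates or exit shares are stated. Nor is the UK date shown to add inequality: first entry was no later than 29 January 2019, so five years from then ends by about January 2024 anyway.
- That person-time would make the results comparable with the parent studies. Patients enter already treated and selected for benefit, and exit for an AE or loss of benefit may be informative. A rate cures neither.
- That the by-visit clinical benefit percentage has the same defect. SAP 4.1 counts non-missing observations, which largely settles that denominator.

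A further objection is that SAP 5.1.2 sets some partial AE dates to the day after treatment start. Those events share the calendar year of treatment start, so they fall in year 1 regardless; a footnote is enough.

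**Conclusion.** The point holds as a worthwhile, inexpensive improvement. Neither document divides any AE count by time at risk, and the design makes time at risk unequal. Crude percentages therefore cannot separate risk from exposure or be compared between PSUR cuts.

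The true size is unknown. At an assumed 20 first events per 100 patient-years, entry date alone accounts for 10.0 percentage points (62.6 − 52.6). The outer bound from the dates used is 45.4 points (62.6 − 17.2), and it needs exit on the day of first approval. These figures rest on a constant rate and a common end date, neither of which the documents establish. In the half-and-half mix the rate stays at 20 because it was assumed constant; that shows what the crude figure loses and is not evidence about this drug. No error rate, power or sample size is affected.

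**What to change.** For the final analysis and any further interim, keep the crude tables and add to SAP 7.4.1:

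1. **First-event rates** for any SAE and each of the five AESI categories: patients with a first event, patient-years at risk, and rate per 100 patient-years with exact 95% CI. Give these overall and by year since roll-over, with numbers at risk. Time at risk runs from the first roll-over dose to the first event, or to the earliest of last dose + 30 days, death, end of observation (withdrawal of consent or loss to follow-up) and data cut-off.
2. **Total-event rates** for any AE, SAEs and AESIs: events per 100 patient-years of the on-treatment period, overall and by year. Count events by the SAP 7.4.1 occurrence rule, because protocol 10.1.1 has a worsening event entered a second time. Give the any-AE first-event rate overall only.
3. **Footnotes**: the number of events left out because the start date is missing (SAP 5.1.2 does not impute it), and the number with an imputed start date.
4. **A statement on interpretation**: year since roll-over is not year since first osilodrostat dose; patients enter already treated and selected for benefit; exit for an AE or loss of benefit may be informative. The rates are therefore not directly comparable with parent-study rates.

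The interims already performed are not affected. The cost is SAP wording and a few extra tables from dates already collected, with no new patients, visits or data. The downside is wide intervals for rare AESIs and late years.
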